5.2.6.2.2 AE reporting to the sponsor and timelines

The investigator must report SAEs, AESIs, and non-serious AEs which are relevant for the reported SAE or AESI, on the BI SAE form via fax immediately (within 24 hours) to the sponsor's unique entry point (country specific contact details will be provided in the ISF). The same timeline applies if follow-up information becomes available. In specific occasions, the investigator could inform the sponsor upfront via telephone. This does not replace the requirement to complete and fax the BI SAE form.

With receipt of any further information to these events, a follow-up SAE form has to be provided. For follow-up information the same rules and timeline apply as for initial information.

Additionally, serious adverse events leading to death, which is related to IMP, should additionally fax to local PV immediately (contact details will be provided in the ISF).

5.2.6.2.3 Information required

All (S)AEs, including those persisting after individual patient's end of trial must be followed up until they have resolved, have been assessed as "chronic" or "stable", or no further information can be obtained.

5.2.6.2.4 Pregnancy

In rare cases, pregnancy might occur in a clinical trial. Once a patient has been enrolled in the clinical trial and has taken trial medication, the investigator must report any drug exposure during pregnancy in a trial participant immediately (within 24 hours) by means of Part A of the Pregnancy Monitoring Form to the sponsor's unique entry point.

Similarly, potential drug exposure during pregnancy must be reported if a partner of a male trial participant becomes pregnant. This requires a written consent of the pregnant partner.

The outcome of the pregnancy associated with the drug exposure during pregnancy must be followed up and reported to the sponsor's unique entry point on the Pregnancy Monitoring Form for Clinical Trials (Part B).

The ISF will contain the Pregnancy Monitoring Form for Clinical Trials (Part A and B) as well as non-trial specific information and consent for the pregnant partner.

As pregnancy itself is not to be reported as an AE, in the absence of an accompanying SAE and/or AESI, only the Pregnancy Monitoring Form for Clinical Trials and not the SAE form is to be completed. If there is an SAE and/or AESI associated with the pregnancy an SAE form must be completed in addition.

5.3 DRUG CONCENTRATION MEASUREMENTS AND PHARMACOKINETICS

Not applicable.

5.4 ASSESSMENT OF BIOMARKER(S)

Not applicable.

5.5 BIOBANKING

Not applicable.

5.6 OTHER ASSESSMENTS

Not applicable.

5.7 APPROPRIATENESS OF MEASUREMENTS

Not applicable.

6. INVESTIGATIONAL PLAN

6.1 VISIT SCHEDULE

The study will consist of three sequential periods, a Screening period of up to 7 days, a treatment period of 8 weeks and a follow-up period of 4 weeks. The maximum duration is expected to be 93 days.

Following an initial screening, eligible patients will be randomized to enter the first 4-week treatment periods in which they will be given Tiotropium Respimat® or Tiotropium HandiHaler® respectively. Before the treatment phase, patients will be trained to use these two inhalers correctly. After the first treatment period, patients will enter the next 4-week treatment phase and have to switch to the other inhaler. After each of the treatment period, patients will fill-in the performance domain, convenience domain and overall satisfaction. After conclusion of both treatment phases (at visit 4), all patients will indicate their preference and willingness to continue of these two inhalers in the PASAPQ.

Adverse events will be tracked from screening to the follow-up period. All SAEs or any AE associated with trial medication persisting after trial completion must be followed up until they have been resolved or have been fully characterized (have been assessed as “chronic” or “stable”, or no further information can be obtained).

6.2 DETAILS OF TRIAL PROCEDURES AT SELECTED VISITS

6.2.1 Screening period(s)

Written informed consent will be obtained prior to initiating any study-related evaluation. Upon obtaining consent, the patient will be instructed on the medication and other restrictions for the screening test.

All tests for the visits during the study period are detailed in the [Flow Chart](#) and completed at local sites.

Screening Period (Visit 1, up to 7 days)

- A complete medical history, including demographic information.
- A complete physical examination including vital sign measurements and 12-lead ECG.
- Smoking status (smoker vs. ex-smoker) will be recorded.
- Concomitant therapy for the two months will be recorded in the CRF.
- Blood and urine samples will be collected for laboratory analysis and determination of eligibility as well as a urine pregnancy for females of child-bearing potential. The patient will perform a baseline pulmonary function test (PFT) that will consist of three manoeuvres and the highest FEV1 and FVC of those manoeuvres will be recorded on the eCRF. The patient will be required to have a post-bronchodilator $30\% \leq \text{FEV1} \leq 80\%$ of predicted normal and $\text{FEV1/FVC} \leq 70\%$. Spirometry must be done at baseline and approximately 1/2 hour following 4 inhalations of albuterol. Predicted normal values will be calculated according to the Jinping Zheng's study [\[R18-2762\]](#). Historical data from

Proprietary confidential information © 2020 Boehringer Ingelheim International GmbH or one or more of its affiliated companies

spirometry measurements within the past 6 months either at the site or at the other hospital may be used. Please refer to [flow chart](#) for details.

- Patients will be assessed for the eligibility as per the inclusion and exclusion criteria.
- Patients will be dispensed a Salbutamol Sulphate Aerosol (pMDI) as rescue medication. The usage guidance will be given.
- The Patient Diary will be dispensed to the patient. Directions will be provided on proper completion.
- Trial Identification Card (TIC) with trial information and study Doctor's contact information will be provided for the patient.
- Patients will be instructed on medication restrictions.
- Details of any patient who is screened for the trial but are found to be ineligible must be entered in an enrolment log and documented in the case report form.

6.2.2 Treatment period(s)

Visit 2 (1 day):

This visit will be scheduled for after the completion of the screening period.

The inclusion and exclusion criteria will be reviewed prior to randomization, and if the patient qualifies for the screen period of the trial, patients will be randomized into 2 groups by envelope randomization. When one group (T1) is randomized into Respimat® arm, and another group (T2) will enter into Handihaler® arm for 4-week treatment.

After randomization the following will be performed:

- Rescue medication and patient diary dispensed at Visit 1 need to be collected.
- Adverse events and concomitant therapy since last visit will be reviewed and recorded on the eCRF.
- Patients will be trained by the investigator to use the randomized inhalers, i.e. Respimat® or Handihaler®. The placebo of each inhaler will be provided for the training to patients, which will follow the instructions in the local product information and demonstration video.
- The tiotropium Respimat® or Tiotropium Handihaler® will be provided to the patients. The patient will assemble (Tiotropium Respimat®, only) and prime his/her assigned inhaler(s) in the presence of the trial staff.
- The first dose of trial medication will be administered at the clinic.
- Patients will be provided with rescue medication and a new patient diary. He/she will be instructed to return to the clinic in 29 days for the next scheduled visit = visit 3.

Visit 3 (28 days ± 1 days): T1 will enter into Handihaler® arm for 4 weeks after the completion of all procedures as listed below; on the contrary, T2 will enter into Respimat® arm for 4 weeks.

- Patients will have to complete the PASAPQ including total score (Q1-13), overall satisfaction (Q14), except for the preference question prior to any other procedures or evaluations.
- Patients' diary will be collected and reviewed for patient compliance.

Proprietary confidential information © 2020 Boehringer Ingelheim International GmbH or one or more of its affiliated companies

- Concomitant therapy and any adverse events since last visit will be checked and recorded on the eCRF.
- All trial medication (used and un-used) will be collected.
- Patients will be trained by the investigator in the use of the next randomised inhalers, i.e. Respimat® or Handihaler®. The placebo of each inhaler will be provided for the training to patients, following the instructions in the local product information and demonstration video.
- The first dose of trial medication should be administered at the clinic. To avoid overdosing, the investigator needs to confirm whether the patient has already taken the medication at home on the day of V3 visit. If so, the patient will not take the first dose of the newly assigned treatment at Visit 3.
- The tiotropium Respimat® or Tiotropium Handihaler® will be provided to the patients. The patient will assemble (Tiotropium Respimat®, only) and prime his/her assigned inhaler(s) in the presence of the trial staff.
- The first dose of trial medication will be administered at the clinic.
- Patients will be provided with rescue medication and a new patient diary. He/she will be instructed to return to the clinic in 29 days for the next scheduled visit = visit 4.

Visit 4 (56 days±1 days).

The following trial procedures must be performed by all completed patients at Visit 4 as well as by all patients who discontinue the study prematurely (prior to 8 weeks of treatment).

- Patients should complete PASAPQ, including total score (Q1-13), overall satisfaction (Q14), preference and willingness to continue (Q15 and Q16) prior to any other procedures or evaluations.
- Patients' diary will be collected and reviewed for patient compliance.
- All trial medication (used and un-used) will be collected.
- Patients will receive a complete final physical examination with vitals.
- 12 lead-ECG should be done.
- Blood and urine samples will be collected for laboratory analysis.
- Pregnancy test (urine) will be performed on applicable female patients.
- Adverse events and concomitant therapy since last visit will be reviewed and recorded on the eCRF.
- Conclusion of Patient participation

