Dispense patient diary	X	X	X	
Dispense trial identification card (TIC)	X			
Collect Respimat® or Handihaler®			X	X ¹
Collect Rescue Medication		X ⁴	X ⁴	X ⁴
Collect and review patient diary		X	X	X ¹
Adverse events		X	X	X ¹
Compliance check			X	X
Concomitant therapy	X	X	X	X ¹
PASAPQ: question 1-14			X	X
PASAPQ: question 15-16				X
Conclusion of Patient participation				X ¹

1. To be completed by all patients including those who discontinue early because visit 4 is the end of study treatment.
2. Visit 5 is the end of study visit.
3. To be dispensed from Visit 1 to Visit 3.
4. Rescue medication should be collected at next visit whether the patient use or not.
5. At Visit 3, the investigator will instruct the patient how to use first study drug intake on site. To avoid overdosing, the investigator needs to confirm whether the patient has already taken the medication at home on the day of V3 visit. If so, the patient will not take the first dose of the newly assigned treatment at Visit 3.
6. Historical data from spirometry measurements within the past 6 months either at the site or at the other hospital may be used. If the measurements are not performed at the trial site a signed copies of the measurement printouts must be provided to the trial site for source data verification. In case several qualifying spirometry measurements are available, the most recent one should be referred to as long as it was not performed during an exacerbation. Patients may not be randomised to the study without the availability of spirometry data at the actual study site.

TABLE OF CONTENTS

TITLE PAGE	1
CLINICAL TRIAL PROTOCOL SYNOPSIS	2
FLOW CHART	4
TABLE OF CONTENTS	5
ABBREVIATIONS	9
1. INTRODUCTION	11
1.1 MEDICAL BACKGROUND	11
1.2 DRUG PROFILE	11
1.3 RATIONALE FOR PERFORMING THE TRIAL	12
1.4 BENEFIT - RISK ASSESSMENT	13
2. TRIAL OBJECTIVES AND ENDPOINTS	14
2.1 MAIN OBJECTIVES, PRIMARY AND SECONDARY ENDPOINTS	14
2.1.1 Main objectives	14
2.1.2 Primary endpoint(s)	14
2.1.3 Secondary endpoint(s)	14
3. DESCRIPTION OF DESIGN AND TRIAL POPULATION	15
3.1 OVERALL TRIAL DESIGN AND PLAN	15
3.2 DISCUSSION OF TRIAL DESIGN, INCLUDING THE CHOICE OF CONTROL GROUP(S)	15
3.3 SELECTION OF TRIAL POPULATION	15
3.3.1 Main diagnosis for trial entry	16
3.3.2 Inclusion criteria	16
3.3.3 Exclusion criteria	17
3.3.4 Withdrawal of patients from treatment or assessments	18
3.3.4.1 Discontinuation of trial treatment	18
3.3.4.2 Withdrawal of consent to trial participation	19

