4. TREATMENTS

4.1 INVESTIGATIONAL TREATMENTS

4.1.1 Identity of the Investigational Medicinal Products (IMPs)

The test product Tiotropium Respimat® (Spiriva® Respimat®), and the comparator product Tiotropium Handihaler® (Spiriva®) will be supplied by Boehringer Ingelheim Pharma GmbH & Co. KG, Germany. The composition of the drugs is described as follow:

Table 4.1.1:1 Test product: Tiotropium Respimat® (Spiriva® Respimat®)

Substance:	Tiotropium
Pharmaceutical formulation:	inhalation solution
Source:	Boehringer Ingelheim Pharma GmbH & Co. KG, Germany
Unit strength:	2.5µg per puff, 60 puffs with 1 Respimat® Inhaler
Posology:	5 µg once daily, given as 2.5µg per puff, two puffs
Method and route of administration:	Oral Inhalation via Respimat®

Table 4.1.1:2 Comparator products: Tiotropium Handihaler® (Spiriva®)

Substance:	Tiotropium
Pharmaceutical formulation:	Inhalation Powder
Source:	Boehringer Ingelheim Pharma GmbH & Co. KG, Germany
Unit strength:	30 capsules with 1 Handihaler® device
Posology:	18µg once daily
Method and route of administration:	Oral Inhalation via Handihaler®

Proprietary confidential information © 2020 Boehringer Ingelheim International GmbH or one or more of its affiliated companies

Tiotropium Respimat® and Tiotropium Handihaler® both have the same active ingredient in the medicine: tiotropium bromide.

Tiotropium Respimat® delivers a very slow-moving mist that is designed to help the patient inhale the medicine easier. The amount of medicine the patient takes in does not depend on how fast they are able to inhale. Patients receive one dose per day, which lasts for 24 hours.

The medicine in Tiotropium Handihaler® comes in a dry powder contained in a capsule that is put into a special inhaler. The patient takes the medicine by breathing in two inhalations through the Handihaler®. The medicine lasts for 24 hours, so patients take one dose (two inhalations) of Tiotropium Handihaler® per day in the morning. Patients use a new capsule for each dose.

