4.1.2 Selection of doses in the trial and dose modifications

Tiotropium Respimat® and Tiotropium Handihaler® have been available on the market, so dose selection please follow the local package inserts, that is, randomized patients will receive tiotropium 5 µg inhalation solution from the Respimat® inhaler or tiotropium inhalation capsules 18 µg delivered by the HandiHaler®.

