4.1.4.1 Instructing the patient

Detailed written instructions and training for the use of the Respimat®, Handihaler® and Salbutamol Sulphate Aerosol will be given to the patient at Visit 2 and 3 (see [Section 10.1](#), [10.2](#) and [10.3](#)).

The Respimat® inhalers and cartridges will be dispensed to patients unassembled and packaged in one box (each box containing one Tiotropium Respimat® inhaler and one Tiotropium Respimat® cartridge), and patients will be instructed on how to prepare the inhaler for use, including inserting the cartridge into the inhaler and priming the unit, and on using the Tiotropium Respimat® inhaler.

Note: Patients who are randomized to Tiotropium Respimat® must follow the instructions for this inhaler in Section 10.1. These patients must be instructed to take two puffs of Tiotropium Respimat® one time a day.

Patients who are randomized to Tiotropium Handihaler® must follow the instructions for this product according to Section 10.2. These patients must take one capsule of tiotropium bromide once daily with the HandiHaler® device at the same time of day.

Table 4.1.4.1: 1 Dosage and treatment schedule

Treatment	Visit Number	Tiotropium Respimat®	
		μg/daily	
1	Visit 2 - Visit 3 (Week 0-4)	5μg (2 puffs of 2.5μg)	-
	Visit 3 - Visit 4 (Week 4-8)	-	18μg (one capsule)
2	Visit 2 - Visit 3 (Week 0-4)	-	18μg (one capsule)
	Visit 3 - Visit 4 (Week 4-8)	5μg (2 puffs of 2.5μg)	-

The Tiotropium Respimat® contains 60 puffs per cartridge and 2.5μg tiotropium per puff, with drug concentration of 0.2262 mg/ml (calculated as tiotropium) after preparing the inhaler for first use. There is enough medicine for 30 days when it is used as two puffs of Tiotropium Respimat® one time a day.

Each Tiotropium Handihaler® contains 30 capsules with the HandiHaler® device. Each capsule contains 18μg (as tiotropium, equivalent to 22.5μg tiotropium bromide monohydrate), enough for 30 days if used as one capsule once daily with the HandiHaler® device.

Two treatment groups of patients will be assigned to therapy with either Tiotropium

Proprietary confidential information © 2020 Boehringer Ingelheim International GmbH or one or more of its affiliated companies

Respimat® or Tiotropium HandiHaler® for 4 weeks respectively before completing the PASAPQ at a single visit to the study site.

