10.2 INSTRUCTIONS FOR THE USE OF THE HANDIHALER®

Instructions for Use

Introduction

It is the product of tiotropium bromide Spray. Read these Instructions for Use before you start using it.

You will need to use this inhaler only ONCE A DAY. Each time you use it take TWO PUFFS.

Proprietary confidential information © 2020 Boehringer Ingelheim International GmbH or one or more of its affiliated companies

- If Spiriva® Respimat® has not been used for more than **7 days** release one puff towards the ground.
- If Spiriva® Respimat® has not been used for more than **21 days** repeat steps 4 to 6 under 'Prepare for first use' until a cloud is visible. Then repeat steps 4 to 6 three more times.
- Do not touch the piercing element inside the clear base.

[figure not shown]
How to care for your Spiriva® Respimat®

Clean the mouthpiece including the metal part inside the mouthpiece with a damp cloth or tissue only, at least once a week.

Any minor discolouration in the mouthpiece does not affect your Spiriva® Respimat® inhaler performance.

If necessary, wipe the outside of your Spiriva® Respimat® inhaler with a damp cloth.

When to get a new Spiriva® Respimat®

- Your Spiriva Respimat® inhaler contains 60 puffs (30 doses) if used as indicated (two puffs/once daily).
- The dose indicator shows approximately how much medication is left.
- When the dose indicator enters the red area of the scale you need to get a new prescription; there is approximately medication for 7 days left (14 puffs).
- Once the dose indicator reaches the end of the red scale, your Spiriva® Respimat® locks automatically – no more doses can be released. At this point, the clear base cannot be turned any further.
- Spiriva® Respimat® should be discarded three months after you have prepared it for first use, even if it has not been fully used or used at all.

Prepare for first use

1. Remove clear base 
• Keep the cap closed.• Press the safety catch while firmly pulling off the clear base with your other hand.	
2. Insert cartridge 
• Insert the narrow end of the cartridge into the inhaler.• Place the inhaler on a firm surface and push down firmly until it clicks into place.• Do not remove the cartridge once it has been inserted into the inhaler.	

Proprietary confidential information © 2020 Boehringer Ingelheim International GmbH or one or more of its affiliated companies

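### The Visit 3 overdose check looks only at the calendar day, so a patient who used Respimat the previous evening could pass it and be given HandiHaler in clinic less than 24 hours later

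*Protocol*

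**What the plan says.** The Visit 3 rule appears in protocol section 6.2.2 and in footnote 5 of the flow chart. Both give its purpose, the avoidance of overdosing, and its test in one sentence: "the investigator needs to confirm whether the patient has already taken the medication at home on the day of V3 visit". If the answer is yes, the new device is not started at the visit. If it is no, section 6.2.2 has the first dose given in clinic. A later Visit 3 bullet repeats the clinic dose without the condition.

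Dosing times are described differently for the two devices:

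- **Respimat.** Section 4.1.1: "Patients receive one dose per day, which lasts for 24 hours". Section 4.1.4.1: "These patients must be instructed to take two puffs of Tiotropium Respimat® one time a day". The Respimat patient instructions (found under heading 10.2 in the text available): "You will need to use this inhaler only ONCE A DAY". None names a time of day.
- **HandiHaler.** Section 4.1.1: "so patients take one dose (two inhalations) of Tiotropium Handihaler® per day in the morning". Section 4.1.4.1 requires one capsule "once daily with the HandiHaler® device at the same time of day".

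Section 3.2 provides no wash-out between the periods.

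**The concern.** A calendar-day check separates doses reliably only if the daily dose is taken in the morning. For Respimat the visible instructions do not require that. A patient who doses in the evening is following them, truthfully reports no dose on the visit day, and by default is given HandiHaler in clinic.

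At stake is whether a stated safety rule covers a case close to the one it was written for. For such a patient, two once-daily tiotropium products would be taken well under a day apart, once, at the switch.

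**Working it through.** The plan gives no interval or count to reproduce. The check is a comparison of the instructions plus clock arithmetic. The documents give no clock times, so those below are assumptions.

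**1. Does the rule let the case through?** The last Respimat dose is taken on the evening before Visit 3. The test asks only about the visit day, so the answer is no and the clinic dose goes ahead. No other visible section sets a minimum number of hours or says anything about the dose on the evening before the visit.

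**2. How long is the interval?** Assume an evening dose between 18:00 and 23:00 and a clinic dose between 08:00 and 17:00 the next day.

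Interval = (24 − evening hour) + clinic hour

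- Shortest: (24 − 23) + 8 = 9 h
- Longest: (24 − 18) + 17 = 23 h

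With 22:00 as the latest evening dose, the shortest interval is (24 − 22) + 8 = 10 h. Every combination is under 24 h.

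**3. Does the rule treat equal intervals alike?**

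| Last dose | Clinic visit | Interval | Outcome under the rule |
|---|---|---|---|
| 07:00, visit day | 16:00 | 16 − 7 = 9 h | clinic dose withheld |
| 23:00, day before | 08:00 | 1 + 8 = 9 h | clinic dose given |

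The interval is the same and the outcome is opposite.

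**4. Who could be exposed?** Section 7.6 randomises equally to the two sequences, and 71 / 2 = 35.5, so about 35 to 36 patients take Respimat first. This is the size of the sequence, not a count of affected patients. The documents give no share of evening dosers, and that share could be zero. The restriction to this sequence is not watertight either: section 4.1.1 places HandiHaler in the morning, but the operative instruction in 4.1.4.1 asks only for a constant time of day.

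**5. Does it reach the primary analysis?** No. Section 6.2.2 has the PASAPQ completed before anything else at Visit 3, hence before the clinic dose. The next PASAPQ comes four weeks later, at Visit 4.

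**6. What would deferral do?** Assume a morning dose between 07:00 and 10:00. An evening doser deferred to the morning after Visit 3 has:

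- Shortest: 23:00 the day before to 07:00 the day after = 1 + 24 + 7 = 32 h
- Longest: 18:00 the day before to 10:00 the day after = 6 + 24 + 10 = 40 h

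A strict 24 h rule would also catch some regular morning dosers who have not yet dosed on the visit day: 10:00 the day before to 08:00 at the visit is 14 + 8 = 22 h. The trigger should therefore be a dose that day or the previous evening, not a fixed 24 h.

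**The case against.** The regimen is once daily, and overdosing can be read simply as two doses on one day, which the check prevents. No section states a minimum interval. This stands: the 24 hours in 4.1.1 is a duration of effect, not a safety limit. Section 1.2 puts the duration of action above 24 hours, so even doses exactly a day apart overlap. A reader might infer that evening dosers are overdosed or that a 24-hour limit is breached; the documents support neither. What remains is that the rule reacts to a 9-hour gap within one day and ignores the same gap across midnight.

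The visible text also points towards daytime dosing. The first dose is given in clinic at Visit 2, and section 4.1.4.2 speaks of a next scheduled time. This makes the case uncommon. It does not exclude it, because no hour is named.

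Material that is not visible may close the gap. Section 4.1.2 says "dose selection please follow the local package inserts", and training follows the local product information and a demonstration video. Any of these may give a Respimat time. Sections 4.1.4.2 and 4.3 mention only whether doses were taken and how many, but the diary form is not shown and may record a time. The claim is therefore limited to the visible text. Even a recorded time would not help unless the rule told the investigator to act on it.

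Finally, deferral replaces one short interval with one long one. That is true, and it is why regular morning dosing should be the main remedy.

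**Conclusion.** The point holds as a minor gap in an operational safety rule. A patient who took Respimat the previous evening could pass the Visit 3 check and receive the second tiotropium product about 9 to 23 hours later, given the assumed clock times. It concerns mainly the Respimat-first sequence, can occur at most once per patient and is probably uncommon. How many patients it would affect cannot be stated; reading the 35 to 36 Respimat-first patients as affected would be wrong. The documents show no harm and give no harm threshold, and the primary comparison is unaffected. The conclusion assumes that the unseen inserts, video and diary do not already fix a Respimat dosing time.

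**What to change.** **Main change.** In 4.1.4.1, instruct patients on both devices to dose at the same time each morning. The same-day check then does its job, and the two devices carry the same timing instruction.

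**Supporting change.** In 6.2.2 and flow chart footnote 5, ask for the date and time of the last dose. If it was taken that day or the previous evening, start the new device at the next scheduled morning dose. Regular morning dosers who have not yet dosed that day are still dosed in clinic. Make the later Visit 3 bullet on the clinic dose subject to this check; that is a wording correction only.

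**Cost.** One question and one eCRF field at Visit 3, plus short edits in three places. A few first doses of the second device move to the home after placebo training in clinic, which the plan already accepts for same-day dosers. A deferred evening doser has one interval of about 32 to 40 hours, with rescue salbutamol available throughout (section 4.2.1). The main change makes this rare.

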3.3.4.1 Discontinuation of trial treatment

An individual patient will discontinue trial treatment if:

- The patient wants to discontinue trial treatment, without the need to justify the decision.
- The patient has repeatedly shown to be non-compliant with important trial procedures and, in the opinion of both, the investigator and sponsor representative, is not willing or able to adhere to the trial requirements in the future.

Proprietary confidential information © 2020 Boehringer Ingelheim International GmbH or one or more of its affiliated companies

- The patient needs to take concomitant medication that interferes with the investigational medicinal product or other trial treatment.
- The patient can no longer receive trial treatment for medical reasons (such as surgery, adverse events, other diseases, or pregnancy).

In case of a temporary reason, trial treatment should be restarted if medically justified, please see [Section 4.1.4.](#)

Even if the trial treatment is discontinued, the patient remains in the trial and, given his/her agreement, will undergo the procedures for early treatment discontinuation and follow up as outlined in the [Flow chart](#) and section.

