6.2.3 Follow-up Period (84 days±2 days)

During the follow-up period, the investigator should collect AE&SAE information and concomitant therapy by telephone.

Patients who discontinue study treatment early should complete all assessments as soon as possible, which is the same as visit 4, especially, AE check and safety test, such as 12 lead-ECG, Laboratory tests, and so on.

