6.2.4 Removal of patients from therapy assessment

Criteria and rules for stopping subject treatment

To be considered complete, a patient must complete the use of both devices as specified in the protocol without violations of the protocol significant enough to obscure the patient acceptability/preference. Patients who fail to complete all treatment will not be replaced.

Dropouts and Withdrawals

Randomized patients who fail to complete all treatment and all of the testing as specified in the protocol will not be considered complete, may not be enrolled at a later date and will not be replaced. If the investigator feels a subject should be discontinued, the Local Clinical Monitor should be contacted.

A record will be kept of all patients who fail to complete all test-days and their reasons for discontinuation. A final physical examination should be conducted on all discontinued patients. All safety information collected from discontinued patients will be included in the safety analysis of the study.

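### Early discontinuers are told to answer Q15-16 even if they used one inhaler, and no visible rule keeps those answers out; a minor gap in the missing-data sensitivity plan goes with it

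*Protocol*

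**What the plan says.** **Who answers Q15-16.** Protocol 6.2.2 says the Visit 4 procedures must be done by completers "as well as by all patients who discontinue the study prematurely (prior to 8 weeks of treatment"). The first procedure is the PASAPQ, including "preference and willingness to continue (Q15 and Q16) prior to any other procedures or evaluations". Protocol 6.2.3 repeats the rule: "Patients who discontinue study treatment early should complete all assessments as soon as possible, which is the same as visit 4".

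Protocol 6.1 gives a different timing: "After conclusion of both treatment phases (at visit 4), all patients will indicate their preference and willingness to continue of these two inhalers". In Appendix 10.4.2 both items ask the patient to compare the two inhalers used in the study, and Q16 wants a number for each. Protocol 3.3.4.1 says that a patient who stops treatment "will undergo the procedures for early treatment discontinuation and follow up as outlined in the" Flow Chart. There, footnote 1 reads "To be completed by all patients including those who discontinue early because visit 4 is the end of study treatment", and the row "PASAPQ: question 15-16" has a plain X at Visit 4.

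**Who is analysed.** Protocol 7.3 and SAP 6.3 analyse the secondary endpoints on the FAS, which needs one dose of one study drug and one PASAPQ score. SAP Table 6.2:1 excludes a patient from the FAS for missing PASAPQ data only if both visits are missing. SAP 7.5 names a chi-squared test for preference and a model like the primary one for continuous endpoints, and states no denominator. Protocol 6.2.4 does have a two-device concept ("To be considered complete, a patient must complete the use of both devices as specified in the protocol"), but no visible analysis uses it.

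**Missing primary scores.** Protocol 7.5 says the SAP will describe sensitivity analyses that impute according to the reason for missingness. SAP 6.6 leaves visits missed for response-unrelated reasons un-imputed, relies on missing at random, and compares imputed with un-imputed primary data only if imputation occurs. SAP 4 declares no change from the protocol.

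**The concern.** Preference and willingness are comparative. A patient who stopped in period 1 has used one device, so an answer on both is not a comparison of experience. Sites that follow 6.2.2 will collect such answers and sites that follow 6.1 may not, and the analysis set would then admit whatever was collected. Preference is part of the trial's stated objective, and the trial is open-label, so the denominator should be fixed before results are seen.

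On missing data, dislike of a device is a plausible reason to stop in an open-label satisfaction trial. That is the kind of missingness for which the protocol promised an analysis and the visible SAP gives none.

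**Working it through.** **1. Planned size.** Inputs (Protocol 7.7): difference 8, SD of the difference 20, two-sided 5%, 85% power. For the 2x2 crossover t-test the noncentrality is 8/(20/√60) = 3.10 on 58 df, giving power 86.1%; 58 patients give 84.9%. So 60 reproduces. Inflation: 60/0.85 = 70.6, so 71, which leaves 71 − 60 = 11 for non-evaluable data. This is an allowance, not a forecast of period-1 stopping.

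**2. Path of a one-device answer.** A patient stops in period 1, attends the early Visit 4 assessment (6.2.2, 6.2.3), completes Q1-16, has one dose and one PASAPQ score, and so is in the FAS. No visible rule removes the Q15 or Q16 answer. A patient who stops in period 2 after a dose has used both devices and is not affected.

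**3. Effect on Q15.** Assumptions, none stated in the plan: a 50:50 null, 60 two-device patients who all choose a device, and one to three one-device answers all going the same way. Statistic: (a − b)²/(a + b) on 1 df. Example: 38 v 22 gives 256/60 = 4.27, p = 0.039.

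| Prefer Respimat, of 60 | p | one added: Respimat / HandiHaler | three added: Respimat / HandiHaler |
|---|---|---|---|
| 36 | 0.121 | 0.096 / 0.159 | 0.059 / 0.257 |
| 37 | 0.071 | 0.055 / 0.096 | 0.032 / 0.166 |
| 38 | 0.039 | 0.030 / 0.055 | 0.017 / 0.101 |
| 39 | 0.020 | 0.015 / 0.030 | 0.008 / 0.059 |
| 40 | 0.0098 | 0.007 / 0.015 | 0.004 / 0.032 |

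Among Respimat-majority counts, one answer crosses 0.05 only at 38, and three cross only at 37, 38 and 39. Five would widen this to 36 to 40 (36 + 5 v 24: p = 0.035; 40 v 20 + 5: p = 0.063). No-preference answers left out of this test change nothing.

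**4. Effect on Q16.** Assume 60 two-device patients with a mean difference of 10, and three one-device patients whose two numbers differ by g, all in one direction. The simple mean is (600 ± 3g)/63. With g = 30 it is 11.0 or 8.1; with g = 50 it is 11.9 or 7.1.

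**5. Missing primary scores.** Take 60 completers with mean difference 8 and m patients with missing scores whose mean difference is M. Use a common within-group SD, add the between-group spread to the variance, and find the M at which t on N − 2 df just loses significance. Check for m = 11, SD 20, M = −11.4:
- Mean: (480 − 125.4)/71 = 4.99.
- Sum of squares: 69 × 400 + (60 × 11/71) × 19.4² = 27,600 + 3,499 = 31,099.
- SD: √(31,099/70) = 21.1.
- t = 4.99/(21.1/√71), about 2.00, against a critical value of 1.995.

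Over the protocol's SD range of 18 to 22, M runs from −13.8 to −8.9. With m = 4 and SD 20 it is −31.7.

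**The case against.** **The Flow Chart does not settle it.** A reader might infer that the chart exempts discontinuers from the PASAPQ because neither PASAPQ row carries footnote 1. The documents do not support that. The pregnancy-test and compliance rows also show a plain X at Visit 4, yet 6.2.2 asks discontinuers for a pregnancy test and a diary compliance review. The missing footnote is at most supporting evidence. The conflict rests on 6.2.2 and 6.2.3 against 6.1 and the wording of the items.

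**It is not a Protocol-SAP conflict.** The visible SAP does not say who completes Q15-16, so the inconsistency lies inside the Protocol. Nor does the completer definition in 6.2.4 contradict the FAS, because it does not define an analysis set.

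**The exposure is narrow.** It needs a period-1 stopper who attends and answers items that plainly presuppose two inhalers. Q15 also offers a no-preference box, though Q16 has no equivalent. There are no key secondary endpoints. A single illustration at 38 of 60 would overstate fragility, because that is the most sensitive count. All of this stands and limits the size of the point, but the path in step 2 remains open.

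**On missing data,** SAP 6.6 does separate out response-unrelated missed visits, so a partial rule by reason exists. Parts of the SAP are redacted, so the gap can be claimed only for the visible text. Section 6.6, where the method belongs, is visible and covers a different, conditional comparison.

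**Conclusion.** The point holds in this form. Followed as written, 6.2.2 and 6.2.3 collect Q15-16 from patients who used one device, and the FAS admits those answers to two secondary analyses. The count is unknown. One to three is an assumption, and on that assumption the preference test changes only in a narrow band of results (37 to 39 of 60, under an assumed 50:50 null with all added answers on one side). A reader might infer that the preference result is generally fragile; the arithmetic does not support that. The reason to act is that the answers are not valid comparisons and the remedy is cheap.

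The sensitivity-analysis gap is minor and concerns completeness. It does not show that the primary result is at risk: at the planned 8-point effect, 11 patients with missing scores would have to average about 11 points in favour of HandiHaler to remove significance (SD 20).

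**What to change.** In the SAP:
- Base the main Q15 and Q16 analyses on patients with documented use of both devices, and define that use (at least one documented dose of each is the simplest rule). The device dates in Table 6.1:1 identify candidates; because they are labelled as dates received, check them against the dosing records.
- State that denominator for the chi-squared test, and tabulate one-device answers separately.
- Record the restriction in SAP 4, since Protocol 7.3 specifies the FAS.
- Add one delta or tipping-point sensitivity analysis of the primary endpoint for response-related missing scores, or declare its omission in SAP 4.

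At the next protocol amendment, reconcile the Flow Chart, 3.3.4.1, 6.1, 6.2.2 and 6.2.3 on who completes Q15-16. This can wait, because the SAP rule handles answers collected under either reading.

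The cost is SAP wording and one extra run, with no added patients or visits. The downside is slightly fewer answers and some selection: patients who stopped on their first device, perhaps because they disliked it, drop out of the main comparison. The separate table keeps them visible.
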